## 9.2 Randomization

Randomization will be performed using capabilities of the web-based RedCap system. Eligible patients will be randomized in a 1:1 ratio to intervention versus standard of care, with randomization stratified by hospital. Randomization scheme will be generated by the study statistician.

## 9.3 Planned Interim Analyses

There will be no planned interim analyses with hypothesis testing. Regular assessment of safety parameters will be performed as outlined in Section 7.

## 9.4 Analysis Plan

### 9.4.1 Analysis

Descriptive data will be summarized by treatment group and overall using standard statistical methods. Full details of the planned analyses will be specified in a statistical analysis plan (SAP) which will be completed prior to the database lock.

*Primary analyses*

The primary outcome (antibiotic DOT) will be evaluated using GEE negative binomial regression with treatment as the only covariate, hospital as the cluster variable and assuming compound symmetry covariance structure within the clusters. Model fit will be examined and alternative distributions for the regression model (Poisson or overdispersed Poisson) may be considered.

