#### **Endpoints**

*Primary endpoint:*

- 1) Antibiotic utilization measured as antibacterial Days of Therapy (DOT) among randomized patients.
  - a. Definitions
    - i. Days of therapy (DOT) is defined as the number of calendar days of antibacterial agent exposure. A DOT is counted for any amount of antimicrobial given on that calendar day. For example, administration of cefazolin as a single dose or as 3 doses given 8 hours apart but within the same 24-hour period both represent 1 DOT. Single agents are counted separately and then summed. For example, administration of vancomycin plus ceftazidime on the same calendar day would represent 2 DOT for the same calendar day.
    - ii. Antibacterial agents will be defined by NHSN AU Module antimicrobial category="Antibacterial" (see Appendix 3). Antibiotics added to the NHSN AU option during the study (e.g. if newly FDA-approved), will be added to the study protocol Table as needed.
      1. "Luminal" antibiotics that do not achieve adequate distribution for treatment of systemic infections will be excluded as follows: oral vancomycin, fidaxomicin, and rifaxamin.
      2. Route of antibacterials will be limited to those identified in the NHSN AU module given by digestive, intravenous, inhaled, or intramuscular.
  - b. Measurement of DOT will start one day after randomization to ensure antibacterial agents given prior to randomization are not included in outcome.
  - c. Measurement will include inpatient DOT plus intended post-discharge antibacterial DOT through 30 days post-randomization.
    - i. Post-discharge antibacterial DOT will be limited to the planned DOT/duration at the time of discharge
    - ii. DOT associated with readmissions during the 30-day post-randomization period will not be included in the primary endpoint, but will be included in measurement of adverse events.

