1. Patient characteristics: age, gender, race, admission and discharge dates, location prior to admission (e.g. transfer from another facility or skilled nursing facility), prior hospitalization in the last 90 days, prior surgery within the last 30 days, ICU admission date (if applicable)
  - a. Length of stay during index admission
  - b. Length of stay prior to enrollment
2. Primary and secondary diagnoses (by ICD-10 code)

3. Methods for implementation of the protocol, including centralized versus de-centralized pharmacist and communication method.
4. Outpatient and/or post-discharge antibiotic exposures in the 30 days post randomization.

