### ***Data Collection Strategy and Sources***

Data will be collected using two strategies to best integrate data available from routine care within the electronic health record and daily routine activities of the hospital pharmacist: electronic data and data manually entered into a REDCap database.

Electronic Data - The majority of data will come from existing datasets collected as part of clinical operations. Electronic data extracts will be prepared from each hospital's electronic systems according to a pre-specified data dictionary for each of the primary and secondary outcomes and additional data outlined above. The primary outcome will be measured directly from electronic medication administration records (eMAR) which captures the location, administration date/time, and agent used. Additional endpoints will be extracted from billing, administrative, and laboratory data and will emulate files previously collected for DETOURS-Retro (Pro00076818). Key difference in data collected with the trial as opposed to DETOURS-Retro is that datasets for this trial will include PHI including MRN in order to adequately link outcomes captured in electronic data extracts with manually collected data.

REDCap Data – Data specifically collected on eligible patients (Pass Step 1 of Opt-Out Protocol) will be entered into a REDCap database. Data collected from eligible patients will include the result of the Safety Checklist (Step 2) and indication(s) for failure if applicable. For patients who pass the Safety Checklist, additional data will be entered for the result of the Opt-Out Procedure (Step 4) among patients randomized to intervention. Finally, rationale for opt-out will be entered for applicable patients (Step 5). These data, including proportion of eligible patients randomized to intervention and result of Opt-Out Procedure, will be regularly analyzed and fed back to sites as the study progresses.

Institutions will be able to decide for themselves what is the most effective way to document reviews and interventions.

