The data analysis was performed using GEE negative binomial regression with treatment as the only covariate, hospital as the cluster variable and assuming compound symmetry covariance structure within the clusters.

With these assumptions, power ranged from 28% for 10% reduction to >99% power for 40% reduction in mean DOT.

Decrease in mean DOT	Power
10%	28%
20%	66%
25%	87%
30%	96%
40%	>99%

Using these calculations, target enrollment was set at n=762, giving us 87% power to calculate a 25% decrease in mean DOT. Power for the secondary outcome (DOOR/RADAR) will be calculated after SA3 and 4 are completed.

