## 10 LIMITATIONS AND POTENTIAL SOLUTIONS

The study has potential limitations. First, there may be a temporal bias over the study period. We will consider using regression adjustment for time period to account for this potential limitation and will include additional adjustment factors if residual confounding is detected. Our randomization scheme will decrease this bias as equal numbers of intervention and control patients will be included in all time periods. Second, contamination between arms is possible if a prescriber “learns” during interaction with an intervention patient and then applies the knowledge to a control patient. We believe this is unlikely based on long-standing experience with post-prescription review processes through standard stewardship interventions. Nevertheless, we will collect antimicrobial utilization data for 12-month “pre”-study period that can be used as a baseline comparator. In the event that control patients have a lower DOT than similar patients in the pre-study period, additional analyses will be considered to investigate time bias vs. contamination vs. impact of additional stewardship activities. Though unlikely to occur, if we have difficulty recruiting study hospitals, we will approach additional DASON or Epicenter hospitals.

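### The primary DOT model is fixed with treatment as its only covariate, forgoing a cheap gain in precision from baseline antibiotic exposure that should be derivable from the eMAR

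*Protocol*

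**What the plan says.** Section 9.4.1 gives the primary model as "GEE negative binomial regression with treatment as the only covariate, hospital as the cluster variable", with a compound symmetry structure. The power calculation in Section 9.1 uses the same model, and Section 9.4.1 carries it over to the secondary DOT and LOT outcomes. Full details are left to the SAP, but the covariate set is not left open.

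The endpoint in Section 5.1 counts each agent separately on each calendar day and then sums, so two agents on one day give 2 DOT. The start of counting is also fixed: "Measurement of DOT will start one day after randomization to ensure antibacterial agents given prior to randomization are not included in outcome".

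On data sources, Section 5.1 says the primary outcome comes from "electronic medication administration records (eMAR) which captures the location, administration date/time, and agent used". The additional descriptive data in the same section include "Length of stay prior to enrollment".

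Section 10, in discussing temporal bias, says the study will consider adjusting for time period and "will include additional adjustment factors if residual confounding is detected".

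Section 9.1 states "target enrollment was set at n=762", "giving us 87% power to calculate a 25% decrease in mean DOT". Across the effects considered, "power ranged from 28% for 10% reduction to >99% power for 40% reduction in mean DOT".

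**The concern.** Every randomized patient is already on broad-spectrum therapy, but the number of agents can differ. DOT sums over agents, so while a regimen is unchanged a patient on two agents accrues DOT at twice the daily rate of a patient on one. The number of agents just before randomization is therefore a plausible predictor of the outcome.

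With a log link, randomized treatment and a constant effect, the mean ratio is collapsible. Adjusting for a true baseline covariate then keeps the same estimand and narrows its interval. Precision matters most if the true effect is nearer 20%, where the protocol's own power is only 66%.

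The Section 10 clause works the other way. It lets factors enter after the data are seen, with no list of candidates and no rule for detection. If it were applied to the primary comparison, the choice of covariates would be open to selection.

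**Working it through.** **Inputs from the protocol (Section 9.1).** Control mean 11.4; negative binomial scale k = 1.68; N = 762, taken as 381 per arm (1:1); target ratio 0.75.

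**Assumed.** Two-sided alpha of 0.05 (the power section gives none), and the share of DOT variance explained by baseline, R², for which the protocol has no figure.

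**Dispersion.** Variance = 11.4 + 1.68 × 11.4² = 229.7, so the SD is 15.2, or 1.33 times the mean.

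**Reproducing the plan's figure.** Simulating the protocol's model (ten hospitals with the Table 4 sizes, GEE negative binomial, treatment only, robust z-test, 800 runs less about 5% that did not converge) gives 87.5% for a 25% reduction, against 87% stated. For a 20% reduction it gives 70%, against 66%.

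The closed form is

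SE(log ratio) = √{[(k + 1/μ₀) + (k + 1/μ₁)] / 381}

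- Ratio 0.75, μ₁ = 8.55: √[(1.7677 + 1.7970)/381] = 0.0967. Power = Φ(0.2877/0.0967 − 1.96) = 84.5%.
- Ratio 0.80, μ₁ = 9.12: SE = 0.0966. Power = Φ(0.2231/0.0966 − 1.96) = 63.7%.

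The planned model therefore delivers about what the protocol says it does.

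**With a baseline covariate.** Multiply the SE by √(1 − R²); the equivalent sample size is 762/(1 − R²).

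| R² (assumed) | SE at 0.75 | Power, 25% reduction | Power, 20% reduction | Equivalent N |
|---|---|---|---|---|
| 0 | 0.0967 | 84.5% | 63.7% | 762 |
| 2% | 0.0958 | 85.2% | 64.5% | 778 |
| 5% | 0.0943 | 86.2% | 65.9% | 802 |
| 10% | 0.0918 | 88.0% | 68.2% | 847 |
| 20% | 0.0865 | 91.4% | 73.3% | 952 |

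For an observed ratio of 0.75, the 95% interval goes from 0.620–0.907 unadjusted to 0.633–0.889 at R² = 20%.

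**An illustrative anchor for R².** Suppose half the patients are on one agent and half on two, with DOT proportional to agents. Group means are then 7.6 and 15.2, the between-group variance is 3.8² = 14.4, and R² = 14.4/229.7 = 6.3%. Power becomes 86.7% (up 2.2 points) and 66.5% (up 2.8 points).

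**Simulation check of the gain.** With a multiplicative covariate explaining about 6%, the simulated GEE with the robust test goes from 86.9% to 89.9% (25% reduction) and from 68.3% to 74.9% (20% reduction). These figures are indicative only, because with ten hospitals that robust test rejected about 11% of the time under no effect. That is a separate matter, which adjustment does not cure.

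**Where the baseline cutoff must fall.** Under Section 4.1.4, randomization is followed by the opt-out procedure, so a same-day stop can lower that day's eMAR count in the intervention arm only. I simulated the one-versus-two-agent case with a true ratio of 0.75, letting a share of intervention patients show one agent fewer on the day of randomization (the share is assumed). Adjusting for that whole-day count moved the ratio to about 0.80 at a 10% share and to about 0.85 at 20%. With no true effect and a 10% share it gave 1.08. The unadjusted ratio stayed near 0.75 (or 1.00). The covariate must therefore be measured strictly before randomization.

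**The case against.** The strongest reply is that nothing is broken. The analysis model matches the power model, the stated 87% is reproduced without adjustment, and an unadjusted randomized comparison is valid. That stands. A reader might infer that the trial is underpowered or its primary test biased for want of a covariate; the documents support neither.

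The gain is also uncertain. Eligibility at 48–96 hours narrows the spread of prior duration. Proportionality of later DOT to baseline agents is doubtful where the intervention stops or narrows therapy. A reader might assume a correlation of 0.5 (R² = 25%), which would give 93.0% and 76.0%, gains of 8 and 12 points. Nothing in the protocol supports that value.

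That the extract covers days before randomization is an inference from the eMAR description and the counting rule. It is a fair one, but no section lists pre-randomization agents as a collected variable. Length of stay before enrollment is collected, but only as a descriptor, and no gain from it has been quantified.

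A reader might also infer that Section 10 flatly contradicts Section 9.4.1. Section 10 discusses a limitation and does not say that the primary model will change. Its trigger is loose and worth confining, but that is a clarification.

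Finally, adjustment is not harmless whatever the covariate. As shown above, agents counted over the whole calendar day of randomization can bias the ratio. That objection holds against such a covariate; a strictly earlier cutoff removes it.

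**Conclusion.** The point holds as an inexpensive improvement. Section 9.4.1 closes the covariate set for a very dispersed count, although a plausible predictor should be available from data already drawn.

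Over an assumed R² of 2% to 20%, the SE falls by about 1% to 11%. Closed-form power rises by about 1 to 7 points at the 25% target and about 1 to 10 points at a 20% reduction. The illustrative one-versus-two-agent case sits at the lower end, at 2 to 3 points. If baseline exposure is not prognostic, the gain is nil.

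These figures rest on two-sided 0.05, equal arms, a constant treatment ratio and the planning dispersion of 1.68. The validity of the planned analysis and its stated power are not in question.

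**What to change.** In Section 9.4.1, replace the treatment-only specification with treatment plus pre-specified baseline covariates:

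- (a) the number of distinct NHSN antibacterial agents given before randomization, counted on the calendar day before randomization or in the 24 hours before the randomization time stamp, and not over the whole calendar day of randomization;
- (b) optionally, log(1 + days from admission to randomization).

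Keep the unadjusted model as a sensitivity analysis, and use the same covariates for the secondary DOT and LOT analyses. In Section 10, limit the clause on adding factors when residual confounding is detected to exploratory analyses. Before fixing (a), confirm that the eMAR extract reaches back to the chosen window.

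The cost is wording in the protocol and SAP, one derived variable and one or two extra model parameters. It needs no further patients and, if the extract covers the window, no new data.

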#### *Power calculations*

Power was calculated using a simulation study. First, we evaluated 6 months of data from three hospitals in our network, including 1 tertiary care center and 2 community hospitals. Eligible patients were defined as follows:

1. Blood cultures drawn and negative
  - a. Except 1 of 2 common skin flora
2. Broad antibiotics at 2-3 days after time of blood culture draw
3. We will define the 2nd calendar day after date of blood culture draw as “screen date”
4. The patient is eligible if they received broad antibiotic on either the screen date (day 2) or the day after (day 3).
5. Located on an inpatient medical, surgical, telemetry, or medical/surgical ward on screen date

The main outcome of interest was DOT after screen date, counting inpatient days of therapy occurring screen date + 1 until discharge, and adding post-discharge DOT as defined in electronic prescriptions upon hospital discharge. Table 4 outlines total enrollment assumptions at study hospitals.

A negative binomial regression model was fitted to the admission-level data on DOT. No difference in DOT was found between different types of wards (Medical/Surgical, Surgical, Medical and Telemetry;  $p=0.39$ ) so the final model included intercept only. Hospital was included as a random effect in the model. Mean DOT was estimated as  $\exp(\text{Intercept}) = \exp(2.43) = 11.4$  days, negative binomial scale as 1.68 and variance of the hospital random effect as 0.12.

**Table 4.** Total enrollment assumptions in 10 study hospitals.

		Enrollment/ month	Months in study	Enrollment estimate
Harvard	Academic	10	15	150
Duke	Academic	10	18	180
Penn	Academic	10	18	180
Presbyterian	Community	2	18	36
Wilson	Community	2	18	36
Iredell	Community	2	18	36
SRMC	Community	2	18	36
Fayette	Community	2	18	36
ATL	Community	2	18	36
Newnan	Community	2	18	36
			total	762

Power was estimated using a simulation study with 500 repetitions. Based on the above assumptions, DOT per admission in the standard care arm were generated in each hospital from a negative binomial distribution with mean=(11.4+hospital effect) and scale=1.68, where hospital effect was generated from a normal distribution with mean 0 and variance 0.12. DOT in the opt-out arm were generated from the same model with the mean=(eff\*11.4+hospital effect), where reduction in mean DOT parameter “eff” ranged in values from 0.9 to 0.6 (i.e. 10%-40% reduction).

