### *Secondary analyses*

Secondary outcome #1 (RADAR/DOOR) will be compared between treatment arms using Wilcoxon rank-sum test. Probability of a better RADAR/DOOR for a randomly selected patient using DETOURS strategy compared with control will be calculated, along with the 95% confidence interval.

Safety outcomes (secondary outcome #2) and process indicators (secondary outcome #3) will be analyzed using summary statistics.

Secondary outcomes including DOT and LOT (secondary outcomes #4, #5, and #6) will be analyzed using the same method as for the primary outcome #1 above.

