### *Subgroup analyses*

Subgroup analyses of the primary outcome will evaluate whether the treatment effect is consistent between 1) medicine patients vs. surgical patients 2) between study hospitals and 3) comparing academic to community hospitals. Additional analyses will compare differences in outcomes and patient/prescriber characteristics for patients in whom protocol-driven de-escalation was implemented versus those in whom the prescriber opted-out of de-escalation. Process indicators for these subgroups will be analyzed using summary statistics.

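### The primary GEE is clustered on about 10 very unequal hospitals; under the usual uncorrected empirical standard error its type I error would be about 11–13%, not 5%

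*Protocol*

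**What the plan says.** Section 9.4.1 of the protocol fixes the primary model as "GEE negative binomial regression with treatment as the only covariate, hospital as the cluster variable", with a compound-symmetry working correlation. The only flexibility it mentions is a change of distribution to Poisson or overdispersed Poisson. Section 9.2 allocates individual patients 1:1 "with randomization stratified by hospital".

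The power simulation in Section 9.1 used the same model: "The data analysis was performed using GEE negative binomial regression with treatment as the only covariate, hospital as the cluster variable". Table 4 ("Total enrollment assumptions in 10 study hospitals") lists three academic sites with 150, 180 and 180 patients and seven community sites with 36 each, 762 in all. The result is that "power ranged from 28% for 10% reduction to >99% power for 40% reduction in mean DOT", with 87% at a 25% reduction.

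For the DOT and LOT secondary outcomes (#4 to #6) the protocol says they "will be analyzed using the same method as for the primary outcome #1 above". Outcome #4 in Section 5.1 includes sub-groups of hospitals, with community versus tertiary care as the example.

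The protocol does not name the variance estimator, the reference distribution, any small-sample correction, alpha or sidedness. It leaves full analysis details to an SAP, which is not at hand.

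**The concern.** GEE inference normally rests on the empirical (sandwich) variance, which is justified as the number of clusters grows. Here the cluster is the hospital and there are about 10, of which three hold 510/762 = 67% of the patients. With so few clusters the empirical variance is biased low and is itself unstable.

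The design does not call for this. Treatment varies between patients within each hospital, so there are hundreds of independent randomized units, and hospital is a stratification factor that can be modelled directly. Clustering on hospital reduces the information about the variance to about 10 contributions.

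At stake is the primary test. Its false-positive rate could be more than twice the nominal level and its confidence intervals too narrow. The same method carries over to secondary analyses with even fewer clusters.

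**Working it through.** **Inputs (Section 9.1).** Control mean 11.4 DOT; negative binomial scale 1.68, read as dispersion k with variance μ + kμ²; hospital effect normal with variance 0.12, added to the mean; hospital sizes as in Table 4; 1:1 allocation within hospital (381 per arm). Two-sided alpha of 0.05 is an assumption, since none is stated.

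**Effective number of clusters.** 762² / (150² + 2×180² + 7×36²) = 580,644 / 96,372 = 6.0.

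**Closed-form benchmark for a valid test.** SE of the log rate ratio = √[(1/μ₀ + 1/μ₁ + 2k)/381].
- Null: √[(0.0877 + 0.0877 + 3.36)/381] = 0.096.
- 10% reduction (μ₁ = 10.26): SE = √(3.545/381) = 0.0965; |ln 0.9|/SE = 0.1054/0.0965 = 1.09; power 19.4%.
- 25% reduction (μ₁ = 8.55): SE = √(3.565/381) = 0.0967; |ln 0.75|/SE = 0.2877/0.0967 = 2.97; power 84.5%.

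**Reproducing the stated power.** Data were simulated from the Section 9.1 model and fitted by the planned GEE. Power in %:

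| Reduction | Stated | Empirical SE, uncorrected, z | Empirical SE with G/(G−1), z | Model-based SE, z | Closed form |
|---|---|---|---|---|---|
| 10% | 28 | 29.9 | 28.6 | 19.8 | 19.4 |
| 20% | 66 | 70.9 | 68.7 | 63.7 | 63.7 |
| 25% | 87 | 86.8 | 85.5 | 84.8 | 84.5 |
| 30% | 96 | 95.8 | 95.0 | 95.5 | 95.8 |
| 40% | >99 | 99.9 | 99.9 | 100 | 100 |

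The protocol used 500 repetitions, so around 20% power the Monte Carlo standard error is √(0.198×0.802/500) = 1.8 points. The stated 28% is (28 − 19.8)/1.78 = 4.6 such errors above the model-based value. That row discriminates clearly and favours sandwich-type inference. The others do not: at 20% the stated 66% is 2.4 Monte Carlo errors below the uncorrected value and nearer the model-based one, and the last three rows fit every column.

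**Type I error and power for a 25% reduction, same data model:**

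| Inference | Type I error | Power |
|---|---|---|
| GEE, uncorrected empirical SE, z | 12.6% (10,000 runs) | 86.8% |
| GEE, empirical SE, t(9) | 8.8% | – |
| GEE, Mancl–DeRouen SE, z | 8.6% | – |
| GEE, Mancl–DeRouen SE, t(9) | 5.1% | about 70% |
| GEE, model-based SE, z | 5.2% | about 85% |
| Negative binomial, hospital fixed effect | 4.5–5.7% | 83–85% |

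Separately coded runs of the first row gave 11.2% to 12.6%, and a standard GEE package gave 12.4% and 12.8% over 500 data sets each. The mean empirical SE under the null is 0.084 against a true SD of about 0.096, some 13% too small. That bias alone would give a rejection rate of 2×Φ(−1.96×0.084/0.096) ≈ 9%; the variability of the SE adds the rest.

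**Sensitivity.** Hospital variance on the log scale: 12.8–13.7%. Scale read as the reciprocal: 12.9%, although that reading gives over 99% power at a 25% reduction and so does not reproduce the table. Ten equal hospitals: 10.2%, so the small number of clusters drives most of the excess.

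**Hospital sub-group.** If the tertiary sub-group is the three academic hospitals of Table 4, null rejection is about 25% with the uncorrected empirical SE and 5.7% with hospital as a fixed effect.

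**The case against.** The strongest reply is that the inflation depends on a choice the protocol does not make. The variance estimator and degrees of freedom are ordinary SAP content. The same GEE with a model-based SE rejects about 5% of the time, and a bias-corrected SE with t(9) also restores the level. This stands as a limit: the point is conditional, and a reader who infers that the stated GEE is invalid under any inference goes further than the document allows.

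It does not dissolve the point. The protocol itself fixes the clustering unit and the covariate set and rests its sample size on that analysis. Its 28% figure is hard to obtain from a valid two-sided 5% test. A bias-corrected SE with t(9) in the SAP would contradict the stated 87% power.

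Three stronger readings are tempting and not supported:
- That the power table proves the uncorrected sandwich was used. A sandwich with the simple G/(G−1) factor fits about as well, though it still rejects 10.1% under the null. A one-sided 5% test also gives about 30% in the 10% row, though it fits the 20% and 25% rows worse.
- That a GEE is prescribed within single hospitals. The subgroup paragraph asks about consistency "between study hospitals and 3) comparing academic to community hospitals" but names no model, so only the grouping by hospital type in outcome #4 inherits the method.
- That hospital is ignored. It is not a covariate, but it enters through the exchangeable correlation.

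**Conclusion.** The concern holds in conditional form. If inference follows the usual GEE default (uncorrected empirical SE, normal reference, two-sided 5%), the primary test has a type I error of about 11–13% under the protocol's own assumptions, and a three-hospital sub-group analysis about 25%. The power table suggests inference of this kind, mainly through its 10% row, but does not prove it. Correcting the GEE with a bias-corrected SE and t(9) brings the level back to about 5% at the price of about 17 points of power for a 25% reduction (87% stated, about 70% obtained).

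The figures rest on the 10 hospitals and sizes of Table 4, dispersion 1.68, and two-sided alpha of 0.05. Section 10 allows further hospitals to be approached if recruitment of sites is difficult; more or more equal clusters would lessen the inflation, but ten equal ones still give about 10%.

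**What to change.** In Section 9.4.1, make the primary model a negative binomial regression of DOT on treatment plus hospital as a fixed effect, with patient-level model-based or patient-level robust standard errors, and state alpha and sidedness. Use the same model for secondary outcomes #4 to #6, and compare hospitals and hospital types through treatment-by-subgroup interactions.

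Restate the power table under this model: about 20% for a 10% reduction and about 84% for a 25% reduction, in place of 28% and 87%.

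The cost is one paragraph in the protocol, matching text in the SAP before database lock, and slightly lower stated power. Hospital is already recorded as the stratification factor, so no new data are needed. If the GEE is kept instead, the protocol should name the variance estimator and reference distribution and give the power that follows from them.
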